7.3.4 Participant termination from the study

Under certain circumstances, an individual participant may be terminated from participation in this study. Specific events that will result in early termination include:

- Participant refuses further participation,
- Participant relocates and remote follow-up or transfer to another HVTN CRS is not possible,
- HVTN CRS determines that the participant is lost to follow-up, or
- Investigator decides, in consultation with Protocol Team leadership, to terminate participation (eg, if participant exhibits inappropriate behavior toward clinic staff).
- Any condition where termination from the study is required by applicable regulations.

8 Study product preparation and administration

CRS pharmacists should consult the Pharmacy Guidelines and Instructions for DAIDS Clinical Trials Networks for standard pharmacy operations. The protocol schema is shown in [Table 3-1](#). See the Investigator's Brochures (IBs) for further information about study products.

8.1 Vaccine regimen

The schedule of vaccination is shown in [Section 3](#) and additional information is given below.

Group 1

Treatment 1 (T1): MPER-656 liposomes, 500 mcg, admixed with Aluminum Hydroxide Suspension, to be administered as two 0.5 mL doses intramuscularly (IM) at months 0, 2, 6, and 12.

Or

Control 1 (C1): Placebo for MPER-656 liposomes (Sodium Chloride for Injection USP, 0.9%) to be administered as two 0.5 mL doses IM at months 0, 2, 6, and 12.

Group 2

Treatment 2 (T2): MPER-656 liposomes, 2000 mcg, admixed with Aluminum Hydroxide Suspension, to be administered as two 0.5 mL doses IM at months 0, 2, 6, and 12.

Or

Control 2 (C2): Placebo for MPER-656 liposomes (Sodium Chloride for Injection USP, 0.9%) to be administered as two 0.5 mL doses IM at months 0, 2, 6, and 12.

8.2 Study product formulation

8.2.1 MPER-656 Liposomes

MPER-656 liposomes will be provided as a frozen liquid in 2 mL borosilicate glass vials. Each vial contains 1.1 mL of MPER liposomes at a nominal concentration of 2.2 mg/mL. MPER-656 liposomes are a homogenous translucent off-white liquid with consistent visual density and without visible phase separation. MPER liposomes are formulated as a sterile, aqueous buffered solution that is filled in single-use glass vials for IM injection.

The product is stored at -25°C to -10°C. The study product is described in further detail in the IB.

8.2.2 Aluminum Hydroxide Suspension (Alhydrogel®)

The Aluminum Hydroxide Suspension will be provided in 3 mL glass vials. Each vial contains 0.7 mL fill volume at a concentration of 5 mg/mL aluminum. The Aluminum Hydroxide Suspension appears as an opaque, white gelatinous precipitate in aqueous suspension.

The product is stored refrigerated at 2° to 8° C. The study product is described in further detail in the MPER-656 liposomes delivered with Alhydrogel® IB.

8.2.3 Placebo for MPER-656 Liposomes (Sodium Chloride for Injection USP, 0.9%)

Sodium Chloride for Injection USP, 0.9% will be used as the placebo for MPER-656 liposomes. The product must be stored as directed by the manufacturer.

8.3 Preparation of study products

Pharmacists should keep in mind that the preparation instructions below are considered medium risk per USP 38 General Chapter Physical Tests / <797> Pharmaceutical Compounding - Sterile, and should follow the requirements of their country, their institution, and their pharmacy regulatory authority regarding these procedures.

Any unused portion of study product will not be used for another participant. Empty vials, unused portion of entered vials, or unused prepared study product should be discarded in a biohazard container and disposed of in accordance with institutional or pharmacy policy.

8.3.1 MPER-656 Liposomes, 500 mcg, admixed with Aluminum Hydroxide Suspension (Group 1)

1. Remove one vial of MPER-656 Liposomes from freezer and equilibrate to room temperature for approximately 30-60 minutes.
2. Remove one vial of Aluminum Hydroxide Suspension from refrigerator and equilibrate to room temperature for at least 5 minutes.
3. Using aseptic technique, withdraw 0.5 mL MPER-656 Liposomes and dispense into a sterile empty glass vial.
4. Using aseptic technique, withdraw 1.4 mL Sodium Chloride for Injection USP, 0.9% and dispense into the vial from Step 3.

5. Resuspend Aluminum Hydroxide Suspension by inverting the vial for 30-60 seconds.
6. Using aseptic technique, withdraw 0.2 mL of Aluminum Hydroxide Suspension and inject it into the vial from Step 4. Gently swirl the vial to mix. Allow formulation to incubate at room temperature for 60 minutes with intermittent gentle swirling or inverting of vial every 15-20 minutes.
7. Using aseptic technique, withdraw 0.5 mL of the mixed preparation into a 1 mL syringe with a 23-25 gauge needle attached. Repeat this step to prepare a second syringe. Prior to administration, gently invert syringes to resuspend admixed product.
8. The admixed product is stable at 2-8° C for four hours, after the 60 minute incubation is complete. Each admixed MPER-656 liposomes and alum dose should be kept refrigerated or on ice and injected within four hours after preparation. The admixed product should be kept on ice during transportation from the pharmacy to the clinic and up until the point of administration.

8.3.2 MPER-656 Liposomes, 2000 mcg, admixed with Aluminum Hydroxide Suspension (Group 2)

1. Remove one vial of MPER-656 Liposomes from freezer and equilibrate to room temperature for approximately 30-60 minutes.
2. Remove one vial of Aluminum Hydroxide Suspension from refrigerator and equilibrate to room temperature for at least 5 minutes.
3. Resuspend Aluminum Hydroxide Suspension by inverting the vial for 30-60 seconds.
4. Using aseptic technique, withdraw 0.1 mL of Aluminum Hydroxide Suspension and inject it into the MPER-656 Liposomes vial. Gently swirl the vial to mix. Allow formulation to incubate at room temperature for 60 minutes with intermittent gentle swirling or inverting of vial every 15-20 minutes.
5. Using aseptic technique, withdraw 0.5 mL of the mixed preparation into a 1 mL syringe with a 23-25 gauge needle attached. Repeat this step to prepare a second syringe. Prior to administration, gently invert syringes to resuspend admixed product.
6. The admixed product is stable at 2-8° C for four hours, after the 60 minute incubation is complete. Each admixed MPER-656 liposomes and alum dose should be kept refrigerated or on ice and injected within four hours after preparation. The admixed product should be kept on ice during transportation from the pharmacy to the clinic and up until the point of administration.

8.3.3 Placebo for MPER-656 Liposomes (Sodium Chloride for Injection USP, 0.9%) (Control 1 and Control 2)

1. Remove one vial of Sodium Chloride for Injection USP, 0.9% from storage.
2. Using aseptic technique, withdraw 0.5 mL of Sodium Chloride for Injection USP, 0.9% into a 1 mL syringe with a 23-25 gauge needle attached. Repeat this step to make a second syringe.
3. The placebo should be kept on ice during transportation from the pharmacy to the clinic and up until the point of administration

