- MPER-peptide-specific immunoglobulin G (IgG) binding antibody (Ab) responses as assessed by binding Ab multiplex assay 2 weeks after the 3rd and 4th vaccination with MPER-656 liposome vaccine

Study products and routes of administration

- MPER-656 liposomes at 0.5 mg/mL with 500 mcg alum (from 5 mg/mL suspension) for two 0.5 mL doses in two sites (total dose of 500 mcg in 1 mL) administered by IM injection in the deltoid muscles (one injection into each deltoid)
- MPER-656 liposomes at 2 mg/mL with 500 mcg alum (from 5 mg/mL suspension) for two 0.5 mL doses in two sites (total dose of 2000 mcg in 1 mL) administered by IM injection in the deltoid muscles (one injection into each deltoid)
- Sodium Chloride for Injection USP, 0.9% administered for two 0.5 mL doses in two sites by IM injection in the deltoid muscles (one injection into each deltoid)

Table 3-1 Schema

Study arm	N	Month 0 (Day 0)	Month 2 (Day 56)	Month 6 (Day 168)	Month 12 (Day 364)
Group 1	5	500 mcg peptide	500 mcg peptide	500 mcg peptide	500 mcg peptide
	1	Placebo	placebo	placebo	placebo
Group 2	15	2000 mcg peptide	2000 mcg peptide	2000 mcg peptide	2000 mcg peptide
	3	Placebo	placebo	placebo	placebo
Total	24 (20/4)				

Note:

Safety data for Group 1 through 2 weeks after the first vaccination will inform whether to proceed with escalation to the higher dose (Group 2).

Participants

24 healthy, HIV-1–uninfected volunteers aged 18 to 50 years; 20 vaccinees, 4 placebo recipients

Design

Multicenter, randomized, dose escalation, placebo-controlled, double-blind trial

Duration per participant

18 months of scheduled clinic visits per participant (main study), followed by an adverse event of special interest (AESI) health contact at month 24

Estimated total study duration

30 months (includes enrollment, planned safety holds, follow-up, and AESI health contact)

Investigational New Drug (IND) sponsor

DAIDS, NIAID, NIH, DHHS (Bethesda, Maryland, USA)

Study product provider

- MPER-656 liposomes: International AIDS Vaccine Initiative, (IAVI, New York, New York, USA)

Core operations

HVTN Vaccine Leadership Group/Core Operations Center, Fred Hutchinson Cancer Research Center (Fred Hutch) (Seattle, Washington, USA)

Statistical and data management center (SDMC)

Statistical Center for HIV/AIDS Research and Prevention (SCHARP), Fred Hutch (Seattle, Washington, USA)

HIV diagnostic laboratory

University of Washington Virology Specialty Laboratory (UW-VSL) (Seattle, Washington, USA)

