4.7.1.6 Rabbit study R25

An early immunogenicity study was performed in rabbits to confirm relevance of this animal model for use in the toxicity study. Only the high dose was used in this study, 2.0 mg of MPER-656 liposomes containing 1.0 mg alum. The data demonstrated that the MPER-656 liposome vaccine was immunogenic, supporting the rabbit as an appropriate model for the GLP toxicity study, and no safety concerns were observed.

Three rabbits received an IM immunization every 2 weeks (for a total of 5 immunizations) with 2 mg of peptide in MPER-656 liposome vaccine formulated with alum (1.0 mg of total aluminum). Bleeds were taken 10 days after each immunization. Results (measured by direct-binding ELISA) for longitudinal binding of serum antibodies from R25 rabbits to the MPER-656 (MPER 656-GTH1) and the 2F5 bnAb epitope (sp62 peptide QQEKNEQELLELDKWASLWN) are shown in [Figure 4-3](#).

[figure not shown]

Figure 4-3 Longitudinal binding by direct-binding ELISA of serum antibodies from R25 rabbits to the MPER-peptide (MPER656-GTH1) and the 2F5 bnAb epitope (sp62). Animals were immunized every 3 weeks, as indicated by arrows. AUC: area under the curve. Horizontal lines indicate the geometric mean.

Immunization with 2 mg of MPER-656 liposome vaccine formulated with alum (1.0 mg total aluminum) induced antibodies in rabbits that bound to the GTH1-656 MPER peptide and the 2F5 bnAb epitope peptide sp62. Sequential vaccinations did not further boost the immune response above that observed following the 1st injection, possibly due to hyperimmunization at 3-week intervals.

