8.4 Administration

All injections are to be given IM in the deltoid, using standard IM injection technique. As there are two injections per visit, one injection will be given in the right deltoid and the other injection will be given in the left deltoid. At sites where registered pharmacists are legally authorized to administer injections, the HVTN CRS may choose to have the pharmacist administer vaccinations.

When preparing a dose in a syringe and administering the dose, consideration should be given to the volume of solution in the needle before and after the dose is administered. Particularly, if the needle used to withdraw the product is replaced prior to vaccine administration, consideration should be given to conserving the full dose of product. The pharmacy and clinic staff members are encouraged to work together to administer the dose specified in the protocol.

If an injection is administered in the contralateral deltoid due to a medical contraindication, the appropriate study staff should document this clearly. Under

this circumstance, this is NOT a protocol violation. Two injections administered into the same deltoid should be documented in the participant's study record.

Any administrator of study product will be blinded to the individual participant's treatment assignment.

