11.2.3 Expedited reporting of adverse events to DAIDS

Requirements, definitions and methods for expedited reporting of AEs are outlined in Version 2.0 (January 2010) of the *Manual for Expedited Reporting of Adverse Events to DAIDS* (DAIDS EAE Manual), which is available on the RSC website at <https://rsc.niaid.nih.gov/clinical-research-sites/manual-expedited-reporting-adverse-events-daids>. The SAE Reporting Category will be used for this study.

The internet-based DAIDS Adverse Experience Reporting System (DAERS) must be used for expedited AE (EAE) reporting to DAIDS. In the event of system outages or technical difficulties, expedited AE reports may be submitted via the DAIDS EAE Form. This form is available on the DAIDS RSC website at <https://rsc.niaid.nih.gov/clinical-research-sites/paper-eae-reporting>.

For questions about DAERS, please contact [contact] or from within the DAERS application itself.

For questions about EAE reporting, please contact the DAIDS RSC Safety Office at ([contact]).

The study products for which expedited reporting are required are:

- MPER-656 liposomes with 500 mcg alum
- Sodium Chloride for Injection USP, 0.9%

While the participant is in the main study reporting period (see Section 3), the SAE Reporting Category will be used.

After completion of the main study period through the completion of the AESI health contact (see Section 3) the Suspected, Unexpected Serious Adverse Reactions (SUSAR) Reporting Category will be used.

After the participant has completed the AESI health contact and is off study, sites must report SUSARs if the study site staff becomes aware of the events on a passive basis (eg, from publicly available information).

The NIAID/DAIDS will report all unexpected SAEs related to the study products observed in this clinical trial to the FDA in accordance with 21 CFR 312.32 (IND Safety Reports). However, because safety is a primary study endpoint, the study sponsor Medical Officer will not routinely be unblinded to study treatment assignment when there is an assessment of relatedness of the SAE with the study product(s); and the safety report will be sent to the FDA based on the blinded attribution assessment.

In some cases, the PSRT or CRS may believe unblinding of the site PI and participant would be appropriate to facilitate the clinical management of an AE or SAE. The HVTN MOP specifies procedures for emergency unblinding, and for early unblinding for medical reasons.

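### Following the Group 2 preparation steps (Section 8.3.2) delivers about 417 mcg alum per vaccination, 16.7% below the 500 mcg stated in Sections 3 and 11.2.3

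*Combined protocol and SAP*

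**What the plan says.** The study product list in Section 3 describes the Group 2 vaccine as "MPER-656 liposomes at 2 mg/mL with 500 mcg alum (from 5 mg/mL suspension"), given as two 0.5 mL injections with a total of 2000 mcg peptide in 1 mL. The Group 1 entry carries the same 500 mcg alum figure. Section 11.2.3 names the product for expedited reporting as "MPER-656 liposomes with 500 mcg alum", with no distinction by group.

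The materials are described in Section 8.2. For the liposomes: "Each vial contains 1.1 mL of MPER liposomes at a nominal concentration of 2.2 mg/mL" (8.2.1). For the adjuvant: "Each vial contains 0.7 mL fill volume at a concentration of 5 mg/mL aluminum" (8.2.2).

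For Group 2, Section 8.3.2 step 4 has the pharmacist "withdraw 0.1 mL of Aluminum Hydroxide Suspension and inject it into the MPER-656 Liposomes vial". No liposome is removed first. Step 5 then draws two 0.5 mL syringes, and Section 8.3 requires unused prepared product to be discarded.

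For Group 1, Section 8.3.1 combines 0.5 mL liposomes with 1.4 mL saline and then says to "withdraw 0.2 mL of Aluminum Hydroxide Suspension and inject it into the vial from Step 4". Two 0.5 mL syringes are drawn from that mixture as well.

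**The concern.** The 0.1 mL alum volume contains exactly 500 mcg, but it goes into 1.1 mL of liposomes and only 1.0 mL of the resulting mixture is injected. The stated alum dose could be met only if nothing were left in the vial, and the steps leave 0.2 mL behind.

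What is at stake is whether the protocol describes the product correctly. A pharmacist who follows Section 8.3.2 exactly cannot deliver the alum amount in Section 3. The gap is built into the instruction, so it recurs at all four vaccinations in the 15-person Group 2 vaccine arm. Alum is a working part of this product: in NHP #208 (Section 4.7.1.5) adjuvant was needed for the highest MPER-binding titers, and the alum-adjuvanted groups received 0.5 mg. The rabbit toxicology groups in Section 4.6.3 also received 500 mcg. A report that quotes 500 mcg for Group 2 would equate the human adjuvant dose with those studies when it was lower.

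**Working it through.** **Inputs**

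- Liposome vial: 1.1 mL at 2.2 mg/mL (8.2.1)
- Alum stock: 5 mg/mL aluminum (8.2.2)
- Group 2: 0.1 mL alum added to the whole vial; 2 × 0.5 mL = 1.0 mL drawn (8.3.2)
- Group 1: 0.5 mL liposomes + 1.4 mL saline + 0.2 mL alum; 1.0 mL drawn (8.3.1)
- Alum is read as aluminum mass. Section 3 ties the 500 mcg to the 5 mg/mL suspension, and Section 4.7.1.6 describes a 1.0 mg alum dose as "formulated with alum (1.0 mg of total aluminum").

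**Formula**

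Delivered amount = volume added × stock concentration × (volume drawn ÷ total mixed volume).

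**Group 2 peptide, to test the inputs.** Total volume is 1.1 + 0.1 = 1.2 mL. Peptide is 1.1 × 2.2 = 2.42 mg, and 2.42 × 1.0/1.2 = 2.017 mg. That is 2017 mcg, 0.8% above the stated 2000 mcg, so these volumes reproduce the plan's peptide dose.

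**Group 2 alum.** 0.1 × 5 = 0.5 mg added; 0.5 × 1.0/1.2 = 0.4167 mg. That is 417 mcg delivered (208 mcg per syringe). The 0.2 mL left behind holds 83 mcg, and 83/500 = 16.7%. The stated 500 mcg is not reproduced.

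**Group 1, for reference.** Total volume is 0.5 + 1.4 + 0.2 = 2.1 mL. Alum is (0.2 × 5)/2.1 = 476 mcg (4.8% low) and peptide is (0.5 × 2.2)/2.1 = 524 mcg (4.8% high). A gap of that size can pass as nominal rounding and is not part of this point.

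**What would make 500 mcg true for Group 2**

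- Liposome volume needed with 0.1 mL alum: 0.5/0.5 − 0.1 = 0.9 mL, against a stated 1.1 mL.
- Alum volume needed with 1.1 mL liposomes: 5v/(1.1 + v) = 0.5, so v = 0.55/4.5 = 0.122 mL, against an instructed 0.1 mL.

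**Sensitivity to vial fill (assumed range; the protocol gives only 1.1 mL)**

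| Liposome volume in vial | Alum delivered | Against 500 mcg |
|---|---|---|
| 1.0 mL | 0.5/1.1 = 455 mcg | −9% |
| 1.1 mL (stated) | 0.5/1.2 = 417 mcg | −16.7% |
| 1.2 mL | 0.5/1.3 = 385 mcg | −23% |

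Alum is short across the whole range.

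**The case against.** The best defence is that 500 mcg was never meant as a delivered dose. Section 3 gives an explicit total only for peptide, Section 8.1 defines the treatments without any alum amount, and Section 11.2.3 is only a product name. On that view 500 mcg is what goes into the preparation. Taken literally this fits Group 2 but not Group 1, where 0.2 × 5 = 1000 mcg goes in under the same wording. A refinement is that Group 1's 2.1 mL makes about two doses, so roughly 500 mcg is compounded per dose in both groups. The documents do not rule that out, but they do not say it either, and it would still leave Group 2 participants receiving 417 mcg under a 500 mcg label.

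A second defence is overfill: 1.0 mL of liposomes plus 0.1 mL alum gives exactly 2.0 mg/mL peptide (2.2/1.1), which suggests a 1.0 mL working volume. Section 8.2.1 says 1.1 mL, however, step 4 uses the whole vial, and the alum would still be 455 mcg.

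Some of the objection stands. The documents give no tolerance for alum, so treating 4.8% as rounding and 16.7% as an error is a judgement. Section 8.4 says staff are "encouraged to work together to administer the dose specified in the protocol", but that paragraph is about solution lost in the needle, so it does not bear directly on the mismatch. Nothing in the documents shows that 417 rather than 500 mcg changes the immune response. Which figure is the intended one may be settled only by the Investigator's Brochure, which was not available here.

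**Conclusion.** The concern holds. On the protocol's own volumes, Group 2 receives 417 mcg alum per vaccination, 83 mcg or 16.7% less than stated. The result assumes nominal fills, full mixing, exactly 1.0 mL injected, and alum expressed as aluminum; within the assumed fill range of 1.0 to 1.2 mL the delivered amount is 455 to 385 mcg.

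The consequence is limited. 417 mcg lies below the 500 mcg given with 2 mg peptide in the rabbit toxicology study, so there is no safety issue. No loss of immunogenicity and no effect on the Group 1 versus Group 2 comparison is claimed. What needs correcting is a contradiction in the stated dose of a product component. It should be fixed, and it is easy to fix.

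**What to change.** First check the Investigator's Brochure for the intended alum amount, then do one of the following.

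- **(a) If 500 mcg delivered is intended,** change Section 8.3.2 step 4 to about 0.12 mL. This gives (0.12 × 5)/1.22 = 492 mcg alum and 2.42/1.22 = 1984 mcg peptide. Exactly 500 mcg needs 0.122 mL, with peptide at 1980 mcg. The 0.7 mL alum vial covers either volume. The sponsor should confirm that the four-hour stability statement still applies. The alum-to-peptide ratio would be 0.60/2.42 = 0.25, between the present Group 2 ratio (0.50/2.42 = 0.21) and the Group 1 ratio (1.00/1.10 = 0.91), both of which already carry that statement.
- **(b) If the present steps are intended,** keep them and state the delivered alum in Sections 3 and 11.2.3: about 476 mcg for Group 1 and 417 mcg for Group 2. Group 1 is restated only so that both groups are described on the same basis.

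Either route needs a clarification memo or letter of amendment before dosing. It changes one volume or two dose statements and adds no participants, visits or procedures.

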8.3.4 Labeling of Study Product

Label the study product as follows and apply an overlay/tape to each syringe to ensure blinding is maintained:

- Participant identifier(s)
- HVTN 133 Study Product or Placebo
- Final volume (mL)
- Route (IM)
- Beyond use date and time
- Any additional information required by jurisdiction

8.4 Administration

All injections are to be given IM in the deltoid, using standard IM injection technique. As there are two injections per visit, one injection will be given in the right deltoid and the other injection will be given in the left deltoid. At sites where registered pharmacists are legally authorized to administer injections, the HVTN CRS may choose to have the pharmacist administer vaccinations.

When preparing a dose in a syringe and administering the dose, consideration should be given to the volume of solution in the needle before and after the dose is administered. Particularly, if the needle used to withdraw the product is replaced prior to vaccine administration, consideration should be given to conserving the full dose of product. The pharmacy and clinic staff members are encouraged to work together to administer the dose specified in the protocol.

If an injection is administered in the contralateral deltoid due to a medical contraindication, the appropriate study staff should document this clearly. Under

this circumstance, this is NOT a protocol violation. Two injections administered into the same deltoid should be documented in the participant's study record.

Any administrator of study product will be blinded to the individual participant's treatment assignment.

